### **6.1.3 Medical history**

Medical history data will be evaluated by frequency tables, showing the number of subjects with medical history findings (i.e., listed conditions of previous diagnoses, diseases, or surgeries based on the CRF) that started before signing of the informed consent and that are considered relevant to the study.

### **6.1.4 Protocol Deviations**

A summary of major protocol deviations will be given by frequency tables showing the number of subjects with major protocol deviations overall, by type of deviation. Analysis will be based on ITT.

Types of major protocol deviations include:

- Significant inclusion criteria not fulfilled
- Significant exclusion criteria fulfilled
- Failure to obtain informed consent before initiation of study procedures
- Prohibited medication use
- Failure to report SAE
- Failure to report outcome event
- Other safety

### **6.1.5 Prior and Concomitant Medications**

Frequency tables by type of medication will be provided for prior medications prior to stroke (for antiplatelets and anticoagulants) and prior to randomization (for all) and separately for concomitant medication continued after randomization, for visits every 12 months, at EOT and post-baseline, i.e. counting every medication that was taken at least once on or after randomization. Analyses will be by treatment group and overall based on ITT.

Prior and concomitant medications from the “Concomitant Medications report CRF 350” will be analyzed according to the given categories. Other concomitant medication will be coded by Anatomical Therapeutic Chemical (ATC) classification system according to the World Health Organization Drug Dictionary (WHO-DD) using the version as outlined in the Trial Summary (TS) domain and listed in section 16 of CSR.

Separately the number of patients receiving ASA at any time-point after randomization and before last dose of study drug will be displayed distinguishing ASA doses of <=100 mg and >100mg.

**6.1.6 Extent of Exposure and Compliance - amended**

All analyses related to intake of study medication will be by treatment group and overall based on SAF.

The treatment duration will be calculated (date of last study medication- date of first study medication+1 day) and analysed descriptively. Additionally the number of subjects by treatment duration category will be given. Categories will include all subjects with at least 3 months, 6 months, 9 months, 12 months, 18 month, 24 month treatment duration.

The time on study medication will be calculated (treatment duration excluding days off study medication) and analysed descriptively.

The number of tablets taken will be calculated (tablets dispensed-tablets returned) and analysed descriptively, as well as corresponding extent of exposure (number of tablets taken\*dose).

$$\text{Compliance (\%)} = \text{MIN}(\text{Compliance\_Riva}, \text{Compliance\_ASA})$$

$$\text{Compliance\_Riva (\%)} = \frac{\text{Number of Riva tablets taken} \times 100}{\text{Number of days with planned tablet intake}}$$

$$\text{Compliance\_ASA (\%)} = \frac{\text{Number of ASA tablets taken} \times 100}{\text{Number of days with planned tablet intake}}$$

Number of tablets taken = 2x110 – returned tablets of pack 1 – returned tablets of pack 2 (+ tablets of unscheduled resupply – returned tablets of resupply)  
(two bottles of medication for each of the medications: Riva/ASA)

Number of days with planned tablet intake = visit date – medication start date +1 (– number of days with temporary interruption)

Compliance will be tabulated as entered in the CRF and summarized for the whole study. The number of subjects with at least 80% compliance will be presented.

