5.2 Discontinuation of patients from study treatment - amended

An excessive rate of patient discontinuations from either treatment or “drop-outs” from the study may render the trial non-interpretable. In this study, outcome events and vital status data are crucial to the primary analysis and must be collected until the end of the study, even if patients are no longer taking study medication. **Therefore, all efforts will be taken to**

¹⁹ Criterion revised with global Protocol Amendment 5. See Section 13.1 for details.

motivate patients to comply with all study procedures and to continue to be followed until the end of the trial.

Patients may discontinue study medication at their own request and without giving reasons (even though providing a reason is encouraged), based on the investigator's judgment, if the patient is pregnant, or at the request of the sponsor (exceptional circumstances). In case a patient is diagnosed with atrial fibrillation with an episode of at least 6 minutes during the study trial medication must be stopped (see section 6.9.2).²⁰ **Study drug will not be routinely discontinued in participants reaching a potential outcome event unless there is a safety concern or a clear indication for an alternative antithrombotic therapy as determined by the local investigator.**

In case of a temporary study medication interruption²¹ for any reason, study medication will be restarted as soon as medically justified in the opinion of the investigator. There is no defined maximum limit for temporary treatment interruption.

For all patients who permanently discontinue study medication, the patients will still be part of the study, and outcome events and vital status must be reported until the efficacy cut-off date for the study is announced. All safety data will continue to be collected for 1 month after the last study medication intake (safety follow-up visit). The investigator and patient must discuss and determine further follow-up options. Options for follow-up are listed below, in descending order of preference:

1. Patient continues the regular study clinic visits at the investigator's site as outlined in the protocol
2. Patient will be contacted by phone at the regular follow-up intervals
3. Patient allows his/her general practitioner or a family relative to be contacted (if allowed in respective country) at the regular follow-up interval
4. Patient will be contacted once at the end of the study

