#### **4.6 Determination of sample size**

The study is event-driven and it is estimated that 7000 patients (3500 per treatment group) need to be randomized in order to have approximately 450 patients experiencing a confirmed primary efficacy outcome event using the ITT data scope. This number of events will allow the demonstration of superiority of rivaroxaban compared to ASA with regard to the primary outcome with a power of 90% and a one-sided level of significance  $\alpha=0.025$  under the following assumptions:

- An average yearly event rate of the composite primary efficacy outcome of 3.8% in the ASA group (4.0% for patients with age  $\geq 60$  years, 2.0% for 10% of patients with age  $< 60$  years)
- Effect size: A 30% RRR for stroke and systemic embolism in the rivaroxaban group compared to ASA
- Length of the recruitment period is 2 years and the total study duration is 3 years

- Approximately 10% of patients will permanently discontinue study medication in the first year and 7% in following years
- Approximately 5% of patients with a diagnosis of AF will switch to standard treatment during study conduct
- Approximately 3% patient deaths per year and 1% of patients lost to follow-up per year

Under these assumptions the expected RRR to be observed in this study would be 26% for the primary efficacy outcome.

The number of patients enrolled may be adjusted and the study duration may be adapted based on a blinded review of the observed overall event rate of confirmed primary efficacy outcomes during the study.

Sample size estimation was based on a Statistical Analysis Software (SAS) macro provided by [Shih](#).

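### The SAP compliance formula does not end planned intake at a permanent stop, so patients who took every tablet until they stopped can be counted below 80%

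*SAP*

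**What the plan says.** SAP 6.1.6 defines compliance for each of the two tablets as tablets taken divided by planned days, and takes the lower of the two. The components are:

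- Denominator: "Number of days with planned tablet intake = visit date – medication start date +1", from which only the days of temporary interruption are then subtracted.
- Numerator: "Number of tablets taken = 2x110 – returned tablets of pack 1 – returned tablets of pack 2", with an adjustment for any unscheduled resupply.
- Reporting: "Compliance will be tabulated as entered in the CRF and summarized for the whole study", and "The number of subjects with at least 80% compliance will be presented". Analyses of drug intake in this section are by treatment group and overall, in the safety analysis set.

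Exposure in the same section is handled differently: "The treatment duration will be calculated (date of last study medication- date of first study medication+1 day) and analysed descriptively". SAP 4.5.1 defines the date of the last double-blind dose and, for patients who stop permanently, takes it from the discontinuation/restart CRF.

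Four Protocol sections determine when a stopper is next seen:

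- Section 5.2 ranks the follow-up options after a permanent stop. The most preferred is "Patient continues the regular study clinic visits at the investigator's site as outlined in the protocol". The section sets no maximum length for a temporary interruption.
- Section 6.9.2 requires a permanent stop for AF seen on a 12-lead ECG or lasting 6 minutes or more on monitoring. It keeps patients who move to open-label rivaroxaban on the regular visits.
- Section 7.1.2.3 places drug return and the compliance record at the 6-monthly visits.
- Section 7.1.2.4 asks patients who stop and will no longer attend the site to come promptly for an end-of-treatment (EOT) visit.

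**The concern.** The formula subtracts one kind of time off drug and is silent on the other. If it is applied as written, every day between a permanent stop and the visit counts as a planned day on which no tablet was taken. A patient who took every tablet until a stop that the protocol itself required can then be classed as poorly compliant. A patient with the same tablet count and the same days off drug, recorded as an interruption, is classed as fully compliant.

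The compliance table would then mix adherence while on drug with discontinuation. If the arms stopped drug at different rates, the table could show a difference in compliance with no difference in how patients took their tablets. Unequal stopping is plausible, because SAP section 1 reports more major bleeding on rivaroxaban and Protocol 6.9.5 lists discontinuation among the responses to serious bleeding. The documents do not show that it happened.

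**Working it through.** The documents give no compliance result, so there is no figure to reproduce. The check applies the formula directly.

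**Inputs.** The formula, the 2x110 supply and the 80% cut-off come from SAP 6.1.6. The 6-month interval comes from Protocol 7.1.2.3 and is taken as 183 days. SAP 4.6 gives 7000 patients, 2 years of recruitment, 3 years in total, and "Approximately 10% of patients will permanently discontinue study medication in the first year and 7% in following years".

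**Step 1: one interval.** For a patient who takes one tablet of each drug daily until day d, with the visit on day v, compliance = 100 × d / (v − temporary interruption days). With v = 183:

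| Last dose on day | Formula as written | Denominator ended at last dose |
|---|---|---|
| 30 | 30/183 = 16.4% | 100% |
| 90 | 90/183 = 49.2% | 100% |
| 146 | 146/183 = 79.8% | 100% |
| 147 | 147/183 = 80.3% | 100% |

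At a first regular 6-month visit, a fully adherent patient who stops on or before day 146 is counted below 80%.

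**Step 2: permanent against temporary.** Take 90 tablets, then 93 days off drug, with the visit on day 183. As a permanent stop this is 90/183 = 49.2%. As a temporary interruption it is 90/(183 − 93) = 100%.

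**Step 3: when the error crosses the cut-off.** Let g be the days from last dose to the visit. Then d/(d + g) < 0.80 exactly when d < 4g. For g = 0, no stopper crosses. For g = 7, 14 or 30, those who stop before day 28, 56 or 120 cross. A late stop is tolerant of a long gap: 730 days of full intake and a 90-day gap give 730/820 = 89%.

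**Step 4: scale under the planning rates.** Assumptions, none fixed by the SAP for this purpose:

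- entry is uniform, so follow-up is 1 to 3 years;
- the stopping hazard is constant at 10% in year 1 and 7% a year later;
- intake is perfect until the stop;
- tablets and days are summed over the whole study;
- deaths, loss to follow-up and the separate AF switch rate are ignored.

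The share who stop is 1 − 0.9 × (1 − 0.93²)/(2 × 0.07257) = 1 − 0.9 × 0.931 = 0.162, where 0.07257 = −ln 0.93. That is about 1135 of 7000. A simulation of this set-up gives:

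| Visit date used for stoppers | Stoppers below 80% | Patients of 7000 |
|---|---|---|
| EOT visit on day of stop | 0% | 0 |
| EOT visit 7 days later | 5% | 56 |
| EOT visit 30 days later | 21% | 238 |
| Next 6-month visit, or end of follow-up if sooner | 52% | 593 |
| Close-out | 85% | 963 |

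Two rows can be checked by hand from Step 3. At +7 days, (1 − 0.9^(28/365.25))/0.162 = 0.0080/0.162 = 5%. At +30 days, (1 − 0.9^(120/365.25))/0.162 = 0.034/0.162 = 21%.

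**The case against.** Four arguments count against the point.

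**The SAP is silent rather than wrong.** A reader might infer that it instructs post-stop days to be counted as missed, so that the result is wrong for every stopper. It does not say that. The denominator is labelled as days on which intake was planned, and after a permanent stop none is planned. Nor does the SAP say which visit date applies to a stopper. This stands as a limit on the claim. It does not remove the gap, because the formula beneath the label leaves those days in.

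**The tabulated value is the CRF value.** The CRF and its completion rules are not in the documents and may already end the count at the stop. This also stands. If they do, the SAP formula misdescribes the calculation; if they do not, the table is distorted. The text needs correcting in either case.

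**The supply and the start date might seem not to match.** The numerator is one 2x110 supply, so if the medication start date meant the first dose, nobody could exceed 220/365 = 60% at 12 months without resupply. The documents do not support that reading. The same section uses a different term for the date of first study medication, and Protocol 7.1.2.3 has drug dispensed and returned every 6 months. The count is most naturally per dispensing interval. What remains is that the SAP states neither the interval start nor the rule for combining intervals.

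**Discontinuation is visible elsewhere.** SAP 6.1.1 reports numbers and reasons for permanent discontinuation by arm, and Kaplan-Meier time to last study medication. SAP 6.1.6 adds treatment duration and time on drug. SAP 6.2.7 repeats the efficacy analyses on treatment. A difference in stopping between arms would show there. This stands, and it is why the point is minor.

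**Conclusion.** The point holds as a minor defect in a descriptive analysis. Applied literally, the formula scores identical tablet intake as 49% or 100% according to whether the time off drug is called permanent or temporary. It also conflicts with the handling of exposure in the same section.

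The share of fully adherent stoppers wrongly placed below 80% runs from none to about 85%. On the planning figures that is 0 to about 963 of 7000 patients. The range reflects the undefined visit date. It rests on the timing assumptions in the working and on the CRF value following the written formula, which cannot be confirmed from the documents.

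A reader might go further and infer that the trial's conclusions are affected. They are not: no test, analysis set or sensitivity analysis uses the 80% cut-off. Excluding temporary interruptions is a legitimate choice if the aim is adherence while on drug. The problem is only that permanent stops are not put on the same footing.

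**What to change.** In SAP 6.1.6:

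1. For each dispensing interval, define planned days = min(visit date, date of last double-blind dose) − start date of that interval's supply + 1 − recorded temporary interruption days within that window.
2. For the whole-study figure, sum tablets taken and planned days over all intervals before dividing, separately for each drug, and then take the lower of the two.
3. Derive both from the recorded dispensing, return and last-dose data, or confirm that the CRF-entered value follows the same rule.

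With this change, a patient with full intake until the stop scores 100% whenever the stop occurs. One residue should be footnoted: SAP 4.5.1 sets a missing last-dose date to the latest logically possible date, so some post-stop days may remain for those patients.

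The cost is a few lines of SAP text and the reprogramming of one descriptive table. No new data should be needed.

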**6.2 Efficacy**

**6.2.1 Primary efficacy variable**

The primary efficacy variable is the time from randomization to first occurrence of any of the components of the composite outcome (adjudicated), including:

- Stroke (ischemic, hemorrhagic, and undefined stroke, TIA with positive neuroimaging)
- Systemic embolism

### 6.2.2 Secondary efficacy variables

The secondary efficacy variables of this study are the time from randomization to first occurrence of:

- Cardiovascular death (CV death; including death due to hemorrhage and death with undetermined/unknown cause), recurrent stroke, systemic embolism, and MI
- All-cause mortality
- Individual components of the primary and secondary efficacy outcomes (stroke, CV death, and MI) as well as ischemic stroke, and disabling stroke (modified Rankin score 4 and 5)

These are listed in the order of sequential testing.

### 6.2.3 Subgroup variables

The following subgroup analyses based on baseline demographics are planned for the comparison of the primary efficacy and safety outcomes:

- Age: <60; 60-75; >75 age (for publication: <75; ≥75 years) additionally <60; ≥60 years
- Sex: male; female
- Race: White; Black; Asian; other
- Region: North America; South America; Western Europe; Eastern Europe; Asia
- BMI: < 25; ≥ 25 to < 30; ≥ 30kg/m^2 (for publication: < 30; ≥ 30kg/m^2)
- Weight: <70; 70-90; >90 kg (for publication: <50; 50-100; >100 kg)
- eGFR: <50; 50-80; >80 mL/min
- Stroke or TIA prior to qualifying stroke: yes or no
- Time from qualifying stroke to randomization: ≤30 days; 30 days to 3 months; > 3months
- Presence of patent foramen ovale: present or absent / not known
- Cardiac rhythm monitoring: <48; ≥ 48 hours  
(≥ 48 hours is fulfilled if in-hospital telemetry was performed and “≥48 hrs” is ticked, or ECG Holter was performed and duration is ≥ 48 hours, or other type of prolonged monitoring was performed or different types of monitoring have been used and total duration is ≥ 48 hours; ranges will be summed up using mid of the range)
- Hypertension: yes or no
- Diabetes: yes or no

Higher absolute efficacy event rates are expected for the following subgroups: older age, females, renal impairment, stroke or TIA prior to qualifying event, hypertension, and diabetes. Even though rivaroxaban has not been tested in patients with ESUS, based on earlier studies with rivaroxaban a consistent (relative) treatment effect across all of the planned subgroups is expected.

A limited number of additional subgroup analyses may be proposed by the Steering Committee.

The randomization was stratified by the dichotomic age group variable for age below 60 years (No/Yes) and by country.

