For 338 participants with cryptogenic stroke whose computed tomography (CT) showed an “embolic topography” the 2 year rate of recurrent ischemic stroke or death was 12% with warfarin vs. 18% with ASA (HR=0.66, 95% CI 0.4-1.2). ⁽⁹⁾

In summary, despite a low therapeutic warfarin anticoagulation range (median INR = 1.9) and limited statistical power, WARSS data from a randomized comparison support the concept that anticoagulation may be substantially more efficacious than ASA for patients with cryptogenic ischemic stroke with embolic features (i.e., those comparable to ESUS patients). In addition, in the PICSS study, 98 participants with a patent foramen ovale, the primary outcome (2 year rate of recurrent ischemic stroke or death) was halved in those assigned to warfarin (9.5% warfarin vs. 17.9% ASA).⁸ ⁽¹⁰⁾

Vitamin K antagonists (VKAs) are not routinely used for cryptogenic stroke/ESUS. A Cochrane Collaboration meta-analysis of trials for secondary prevention in patients with a history of non-cardioembolic stroke of various causes, such as large artery atherosclerosis, intracranial artery stenosis, small penetrating artery disease, and strokes of unknown cause (i.e., cryptogenic stroke) suggested that higher intensity anticoagulation with VKAs could be associated with higher all-cause mortality and major bleeding events. ⁽¹¹⁾

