5.1 Eligibility

5.1.1 Inclusion criteria - amended

1. Embolic stroke of undetermined source (ESUS) defined as:

- Recent ischemic stroke (including TIA with positive neuroimaging) visualized by brain CT or MRI that is not lacunar (i.e., lacunar infarcts are subcortical infarcts ≤ 1.5 cm in the territory of middle cerebral artery or pons; infarcts involving the cerebellum or lateral medulla are not considered as lacunar infarcts). Patients with multiple simultaneous acute lacunar infarcts on DWI imaging may be included. In case of embolic large artery occlusions clearly documented on angiography who undergo successful recanalization, visualization of infarct on neuroimaging is not mandated¹², and
- Absence of cervical carotid atherosclerotic stenosis (or vertebral and basilar artery atherosclerotic stenosis in case of posterior circulation stroke), that is $> 50\%$, or occlusion in arteries supplying the area of ischemia in CT or magnetic resonance (MR) angiography or conventional angiography or ultrasound, and¹³

¹¹ Was 25 to 30 countries prior to global Protocol Amendment 5.

¹² Text was revised with global Protocol Amendment 5. See Section 13.1 for details.

¹³ Bulleted text was revised with global Protocol Amendment 5. See Section 13.1 for details.

- No history of AF, no documented AF on 12-lead electrocardiogram (ECG) or episode of AF lasting 6 minutes or longer detected after ≥ 24 -hour cardiac rhythm monitoring (Holter or telemetry; at least 20 hours acceptable¹⁴), and
 - No intra-cardiac thrombus on either transesophageal or transthoracic echocardiography¹⁵, and
 - No other specific cause of stroke identified by routine clinical care (e.g., arteritis, dissection, migraine/vasospasm, drug abuse)
2. Time from recent ischemic stroke to randomization and first study medication intake (and only if the investigator regards it as safe to initiate therapy with an anticoagulant) between 7 days and 6 months except:
 - in case of minor strokes (NIHSS ≤ 3), study medication may be initiated as early as 3 days after stroke onset.
 - in case of intravenous thrombolysis treatment or hemorrhagic transformation seen on the qualifying CT or MRI, study medication will not be initiated before 10 days after the acute stroke event unless a repeat CT or MRI scan performed before randomization documents the absence of new or extension of hemorrhage.

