5.1.2 Exclusion criteria - amended

1. Severely disabling stroke (modified Rankin score ≥ 4 at screening)
2. If imaging of intracranial arteries is performed by CT or MR angiography or transcranial Doppler: $> 50\%$ luminal stenosis or occlusion in arteries supplying the area of ischemia¹⁸
3. Patent foramen ovale with plans for closure
4. Known serious infection or inflammatory disease that may be the cause of stroke

¹⁴ Global Protocol Amendment 5 added the allowance of monitoring for at least 20 hours to reflect routine practice.

¹⁵ Transesophageal was added with global Protocol Amendment 5.

¹⁶ Prior to global Protocol Amendment 5, patients were eligible for inclusion if they were ≥ 18 years of age (or > 18 years based on country). See Section 13.1.1 for additional details.

¹⁷ This criterion was revised with global Protocol Amendment 5. See Section 13.1 for details.

¹⁸ Prior to global Protocol Amendment 5, luminal stenosis or occlusion was $\geq 50\%$. See Section 13.1 for details.

5. Patient has or is intended to receive an implantable ECG loop recorder
6. Indication for chronic anticoagulation based on guideline recommendations or investigator's judgment; e.g., patient with prosthetic mechanical valve, venous thromboembolism, hypercoagulable state
7. Indication for chronic antiplatelet therapy based on investigator's judgment, in which anticoagulation is not a reasonable substitute, or chronic therapy with a conventional non-steroid anti-inflammatory drug (NSAID) for a non-stroke indication
8. Hypersensitivity or any other contraindication listed in the local labeling for ASA or rivaroxaban
9. Active bleeding, major bleeding within last 6 months, high risk for serious bleeding contraindicating anticoagulant or antiplatelet therapy or history of primary intracranial hemorrhage¹⁹
10. Hepatic disease associated with coagulopathy (prothrombin time prolonged beyond the normal range) and clinically relevant bleeding risk including cirrhotic patients with Child Pugh B and C
11. Estimated glomerular filtration rate (eGFR) < 30 mL/min/1.73 m² as assessed at local laboratory within 1 month of screening
12. Life expectancy less than 6 months
13. Concomitant use of strong inhibitors of both cytochrome P450 isoenzyme 3A4 (CYP3A4) and P-glycoprotein (P-gp), i.e., human immunodeficiency virus protease inhibitors and the following azole-antimycotics agents: ketoconazole, itraconazole, voriconazole, or posaconazole, if used systemically

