### 6.2.6 Subgroup analysis

Subgroup analyses for the efficacy and safety outcomes will be performed based on the same analysis sets and data scopes as in the main analyses of the study outcomes. The subgroup analyses will be presented descriptively without formal hypotheses testing. Additionally forest plots will be generated.

Homogeneity of treatment effect in subgroups, both in magnitude and direction, will be assessed by adding a covariate for the subgroup variable and the corresponding treatment-subgroup interaction to the respective (age-group stratified) Cox proportional hazards model used in the main analysis. Additionally the hazard ratio for the treatment effect will be estimated separately within each level of a subgroup variable using the same Cox proportional hazards.

As the number of subgroup analyses may be large, the probability of observing at least one spurious interaction is high despite the lack of a biological or pharmacological basis for expecting an interaction. Thus, any interactions with a p-value below the 5% type I error level in the analysis of primary outcomes will be interpreted as “flags” to prompt further

investigation into the consistency of the pattern within secondary and related outcomes. This further investigation includes the likelihood ratio test proposed by [Gail](#) to test for qualitative interaction.

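### The patent foramen ovale (PFO) subgroup merges absent with not known, which hides how many patients were unassessed and could understate a true interaction

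*SAP*

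**What the plan says.** The subgroup list in SAP 6.2.3 contains "Presence of patent foramen ovale: present or absent / not known". The baseline list in SAP 6.1.2 and the subgroup list in protocol 8.3.1 word it the same way. Other two-level items in these lists are joined by 'or' (yes or no), while most multi-level items use semicolons. The natural reading is therefore two levels: present, against absent and not known combined.

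The entry criteria allow status to be unknown. Protocol 5.1.1 requires "No intra-cardiac thrombus on either transesophageal or transthoracic echocardiography", which is a test for thrombus by either route. No PFO test is listed as an entry requirement. The only PFO exclusion in protocol 5.1.2 is "Patent foramen ovale with plans for closure", so other carriers, diagnosed or not, can be randomised.

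On the status of the result, SAP 6.2.6 states: "The subgroup analyses will be presented descriptively without formal hypotheses testing". It treats "any interactions with a p-value below the 5% type I error level" in the primary outcomes as a prompt for further investigation. SAP 6.2.3 adds that "a consistent (relative) treatment effect across all of the planned subgroups is expected". Neither SAP 6.2.6 nor the sensitivity analyses in SAP 6.2.7 include a separate not-known level or an analysis limited to patients with known PFO status.

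**The concern.** A patient who was never assessed for PFO carries no information on PFO status, yet the coding places that patient with those in whom PFO was not found. If some unassessed patients are carriers and carriers respond differently, the comparison group's hazard ratio moves toward the carriers' hazard ratio and the contrast shrinks.

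The baseline table has the same coding, so the report would not show how many patients are in doubt. A null PFO interaction could then mean that the effect does not vary by PFO status, or that the comparison group was partly untested, and a reader could not tell which. PFO is a subgroup readers will look at: protocol 1.2 lists paradoxical embolism among the sources of ESUS, and protocol 1.3 cites a study of 98 PFO patients in which "the primary outcome (2 year rate of recurrent ischemic stroke or death) was halved in those assigned to warfarin". The subgroup applies to both the primary efficacy and the safety outcomes.

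**Working it through.** **1. The plan's own figure.** The documents give no figure for the PFO subgroup. The nearest anchor is about 450 events for 90% power at one-sided 0.025, with an expected observed risk reduction of 26% (SAP 4.6). With 1:1 allocation, z = |ln 0.74| × √450 / 2 = 0.3011 × 10.607 = 3.194. Power = Φ(3.194 − 1.960) = 89.1%, which reproduces the stated figure. I use 450 events below.

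**2. Formulas.** Let p be the share of patients with known PFO, u the share with unknown status, and q the share of carriers among the unknown. Assume equal aspirin event rates in carriers and non-carriers.
- Carriers in the comparison group: c = u × q / (1 − p)
- Comparison hazard ratio: HR_C = c × HR_carrier + (1 − c) × HR_non-carrier
- Observed ratio of hazard ratios: HR_carrier / HR_C
- SE of the log ratio: square root of the sum of 1/events over the four arm-by-group cells

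**3. Simple range.** These inputs are all assumptions: p = 10%, u = 20% to 60%, q = 20% to 30%, hazard ratios 0.5 and 0.8. The true ratio is 0.5 / 0.8 = 0.625.

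| | u = 20%, q = 20% | u = 60%, q = 30% |
|---|---|---|
| c | 0.04 / 0.90 = 4.4% | 0.18 / 0.90 = 20% |
| HR_C | 0.787 | 0.740 |
| Observed ratio | 0.636 | 0.676 |
| Shift in SE units | 0.05 | 0.22 |
| Flag power, pooled | 25% | 20% |
| Flag power, known status only | 26% | 24% |

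The present group has about 39 of 450 events, and the SE is about 0.36.

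**4. A range consistent with status unknown at random.** In the left column above, PFO prevalence among assessed patients is 10 / 80 = 12.5%, but 20% is assumed among the unassessed, so those inputs are not random missingness. I therefore fix the true prevalence and let the known share apply equally to carriers and non-carriers. The carrier hazard ratio comes from the rates in protocol 1.3, assuming constant hazards: ln(1 − 0.095) / ln(1 − 0.179) = 0.51. The non-carrier hazard ratio of 0.80 is an assumption, and the true ratio is 0.638.

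Central case (prevalence 25%, status known in 50%):
- c = 0.125 / 0.875 = 14.3%; HR_C = 0.80 − 0.143 × 0.29 = 0.759; observed ratio 0.51 / 0.759 = 0.672.
- Log interaction lost: 1 − 0.397 / 0.450 = 12%.
- The present group has about 49 of 450 events. Flag power is 24% pooled and 27% against known-absent patients only.

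Over prevalence 15% to 40% and known share 30% to 90%, undiagnosed carriers make up 2% to 32% of the pooled group. The observed ratio is 0.642 to 0.721, and 1% to 27% of the log interaction is lost. With a non-carrier hazard ratio of 1.0, the loss is 1% to 25%.

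**5. No true interaction.** With 0.74 in both groups, the observed ratio is 1.0 in every scenario and pooling introduces no bias.

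**6. What splitting cannot repair.** Assume echocardiography detects 60% of carriers and prevalence is 25%. The known-absent group then contains 0.10 / 0.85 = 11.8% carriers, and about 10% of the log interaction is still lost.

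**The case against.** The plan labels the level openly, so no reader is told that PFO was ruled out in everyone outside the present group. The contrast can be read as known PFO against no known PFO, and it keeps every randomised patient. The hazard ratio in the present group is untouched by the pooling if positive findings are true. The analysis is descriptive, interactions are only flags, and SAP 6.2.3 lets the Steering Committee propose a limited number of further subgroup analyses. On any of the ranges above, the shift is small beside the standard error. The trial also stopped early (SAP section 1), so with fewer events than planned the precision would be lower still. All of this stands, and it makes the point minor.

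A reader might infer two stronger things that the documents do not support. The first is that the interaction is diluted as a matter of fact. Dilution needs a true interaction, and the plan expects a consistent relative effect. It also needs status to be unknown at random. If assessment depended on age or region, for example, the bias could differ in size or direction. The second is that the protocol shows a larger anticoagulant effect in PFO carriers. Protocol 1.3 gives 98 patients on warfarin or aspirin, with no confidence interval and no comparator group without PFO. The same section also cites a reduction in patients with embolic topography (hazard ratio 0.66, interval 0.4 to 1.2).

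What remains is that the pooled coding hides the number of unassessed patients, and no other planned analysis shows it.

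**Conclusion.** The point holds as a minor, inexpensive improvement. The coding puts patients with unknown PFO status, possibly including carriers, into the comparison group and does not report how many there are. If a true interaction exists and status is unknown at random, the contrast is biased toward none. Under the assumed inputs a ratio of 0.625 is seen as about 0.64 to 0.68. On the wider grid 1% to 27% of the log interaction is lost, 12% in the central case. Prevalence, the share unassessed and the non-carrier hazard ratio are assumptions, because the documents do not give them. Power for the flag is low with or without the change, so the benefit is a result that can be interpreted. The primary analysis and its error control are unaffected.

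**What to change.** - Report three levels (present, absent, not known), with counts by arm, in the baseline table and the subgroup display. SAP 6.1.2 already gives baseline race its own not-reported level.
- Give the treatment-by-PFO interaction among patients with known status, and show the prespecified pooled contrast beside it.
- If the case report form does not separate absent from not assessed, derive not known from the recorded transesophageal and transthoracic data. Protocol 7.1.2.1 has the diagnostic tests for ESUS recorded, and SAP 4.5.5 has a rule for repeated post-baseline echocardiography. This makes the derivation plausible, but the documents do not show that the form supports it.
- If the change is made after unblinding, label it as such.

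The cost is a recode or derivation and a few extra table rows. The downside is that the known-status contrast uses fewer patients, and carriers missed by insensitive echocardiography remain in the absent group.
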